STATISTICAL ANALYSIS PLAN

LIPID-LOWERING REGIMES IMPROVE OXIDATIVE STRESS, TRYPTOPHAN DEGRADATION IN HYPERCHOLESTEROLEMIA CKD PATIENTS

Date of review: 05th May, 2018

All results will be expressed as mean values (mean SD) or median values (median and range).

The statistical differences between the mean laboratory test results patients and control group will be analyzed by ANOVA one-way statistical analysis or by Student's t-test (with Kolmogorov-Smirnov for normality).

The statistical differences in the effect of each therapy on laboratory mean values will be evaluated by one way repeated measure ANOVA with Bonferroni correction or Dunnet T3 correction, if appropriate.

To compare the differences in the median values of laboratory tests between 3 groups, ANOVA one-way will be applied. If there are statistical differences between 3 groups, we will use deeply ANOVA one-way test to analyze which group is different from another group (with Bonferroni if Levene test ≥ 0.05 or Dunnet T3 if Levene test < 0.05).

Correlation analysis between variables will be performed by Pearson's correlation or Spearman's correlation as appropriate.

Statistical analysis will be performed by using SPSS for Windows, version 20.0 (IBM Corporation; Armonk, NY, USA).

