4. METHODOLOGY

4.1. Study design: A prospectively study with clinical trials, 12 months follow up.

4.2. Subject: 30 patients with hypercholesterolemia (LDL-C), stage 3-4 Chronic Kidney Disease, not receiving dialysis and 30 control participants (sex, age-matched)

4.2.1. Inclusion Criteria:

30 patients with following criteria

- CKD in the 3,4 stage (e-GFR: 15-60 ml/min/1.73 m²)
- Presence of proteinuric CKD defined as creatinine clearance >20 ml/min/1.73 m² combined with urinary protein excretion rate >0.3 g/24 h
- LDL cholesterol concentration > 100 mg/dl (2,59 mmol/l)
- Age:
 - + ≥ 50 years old but not treated with chronic dialysis or kidney transplantation
 - + In adults aged 18-49 years with CKD but not treated with chronic dialysis or kidney transplantation, we suggest statin treatment in people with one or more of the following:
 - known coronary disease (myocardial infarction or coronary revascularization)
 - diabetes mellitus
 - prior ischemic stroke
 - estimated 10-year incidence of coronary death or non-fatal myocardial infarction > 10%

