4.2.3. Criteria for control

- 30 aged, sex-matched subject
- Do not have history of diabetes, hypertension, cardiovascular or cerebrovascular disease, renal failure, blood dyscrasias, cancer, retinal vascular disorders
- Current medication with vitamin B6, B12, or folic acid

4.3. Place:

- In Viet Nam: Internal examination room, internal department, Department of Biochemistry of Hue University Hospital.

- In Italy: Department of Biochemistry of Sassari University Hospital

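### Patients and age- and sex-matched controls are compared by tests that ignore the matching, so p-values are conservative and some precision is lost for any marker related to age or sex

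*SAP*

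**What the plan says.** Protocol section 4.2 enrols "30 patients with hypercholesterolemia (LDL-C), stage 3-4 Chronic Kidney Disease", and with them "30 control participants (sex, age-matched"). Section 4.2.3 repeats the matching as "30 aged, sex-matched subject". Neither place gives an age tolerance, a pairing rule or a pair number, so individual and frequency matching both fit the text.

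The SAP, a single unnumbered section, sets the patient-control analysis in one sentence: "The statistical differences between the mean laboratory test results patients and control group will be analyzed by ANOVA one-way statistical analysis", continuing "or by Student's t-test (with Kolmogorov-Smirnov for normality"). It does not say at which visit patients are compared with controls. The only method for dependent data appears in the next statement, on change within a therapy: "The statistical differences in the effect of each therapy on laboratory mean values will be evaluated by one way repeated measure ANOVA". No significance level is stated for any comparison. The only 0.05 in the SAP is the threshold for choosing a post hoc correction ("with Bonferroni if Levene test ≥ 0.05 or Dunnet T3 if Levene test < 0.05").

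Two other places bear on the point. Protocol section 2.4 lists advanced age among the conditions linked to higher oxidative stress. The two numbered objectives in protocol section 3 concern the effects of therapy and the comparison of regimens, not patients against controls.

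**The concern.** Matching on age and sex makes the two groups alike on those factors. If the factors are related to a marker, the part of its variance that they explain no longer contributes to the chance difference between the group means. An independent-samples test still counts that part in its standard error. The test statistic is then too small on average, the true type I error lies below the nominal level, and power is lower than the design could give. Section 2.4 of the protocol makes some relation between age and the oxidative stress markers plausible.

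With 30 people per group, any avoidable loss of precision is worth a look. There is also a practical side: if the matching is one to one, pair membership may be hard to reconstruct unless it is recorded at enrolment.

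**Working it through.** The documents give no power or precision figure for this comparison, so there is nothing to reproduce.

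**Inputs from the documents:** 30 patients and 30 controls, matched on age and sex (protocol 4.2 and 4.2.3); one-way ANOVA or Student's t-test (SAP).

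**Assumptions:** two-sided 5% level; equal SDs, with results in SD units; no missing values; pair correlation ρ of 0 to 0.3. If the matching is exact, is the only source of correlation, and age and sex explain the same share of variance in both groups, then ρ is about equal to that share.

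**One-to-one matching**

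1. Unpaired 95% half-width: t(0.975, 58) × √(2/30) = 2.002 × 0.2582 = 0.517 SD.
2. Paired 95% half-width: t(0.975, 29) × √(2(1−ρ)/30), with t = 2.045.
3. Break-even correlation: 1 − (2.002/2.045)² ≈ 0.04. Below this the paired interval is the wider one.
4. Type I error of the unpaired test: under the null its statistic has variance of about 1−ρ, so the cut-off of 2.002 acts like 2.002/√(1−ρ). That is 2.11, 2.24 and 2.39 at ρ of 0.1, 0.2 and 0.3. The rates in the table come from 100,000 simulated data sets per value of ρ.
5. Power is taken at a difference of 0.736 SD, where the unpaired test has 80% power if the samples are independent.

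| Assumed ρ | Paired half-width (SD) | Unpaired ÷ paired width | Type I error, unpaired | Power, unpaired | Power, paired |
|---|---|---|---|---|---|
| 0 | 0.528 | 0.98 | 5.0% | 80% | 79% |
| 0.1 | 0.501 | 1.03 | 3.9% | 81% | 83% |
| 0.2 | 0.472 | 1.09 | 2.9% | 83% | 87% |
| 0.3 | 0.442 | 1.17 | 2.1% | 84% | 91% |

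The ratio of standard errors alone, 1/√(1−ρ), is 1.05, 1.12 and 1.20 at ρ of 0.1, 0.2 and 0.3. This overstates the gain because pairing cuts the degrees of freedom from 58 to 29. The width ratios in the table allow for that.

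**Frequency matching**

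There are no pairs, and the matching is used by adjustment. A regression on group, age and sex has 60 − 4 = 56 degrees of freedom. The ratio of adjusted to unadjusted width is t(0.975, 56) × √(1−R²) / t(0.975, 58), where R² is the share of variance explained by age and sex and the first t is 2.003.

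| Assumed R² | Adjusted ÷ unadjusted width | Narrower by |
|---|---|---|
| 5% | 0.975 | about 2% |
| 10% | 0.949 | about 5% |
| 20% | 0.895 | about 10% |
| 30% | 0.837 | about 16% |

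**The case against.** The best defence is that nothing shows pairs to exist. Both descriptions of the controls fit group matching, where a paired test would be wrong. This stands, and it is why adjustment for age and sex, rather than pairing, is the default remedy below. It does not rescue the SAP, which names neither.

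Student's t-test might be read to include its paired form. The SAP does not say so, and the method offered beside it, one-way ANOVA, is for independent groups.

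The size rests on a correlation that the documents do not give. This also stands. At zero correlation the planned test is slightly the better one, and a correlation of 0.3 from matching alone would need age and sex to explain about 30% of the variance in patients and controls alike.

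Four stronger readings are tempting, and the documents do not support them:

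- **The published error bars or confidence intervals will be wrong.** The SAP plans none. It reports mean with SD, or median with range, and neither depends on pairing. Only p-values are affected; interval width serves here as a measure of precision.
- **The benefit of matching is lost.** Balance on age and sex, and so control of confounding by them, survives an unpaired test.
- **Every marker loses power.** Markers unrelated to age or sex lose nothing. Kidney function and urine protein differ between the groups by the selection criteria, so power is hardly an issue for them.
- **Using the matching is free.** It costs degrees of freedom, and a paired test loses the whole pair when one value is missing.

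**Conclusion.** The point holds as a modest one. Followed as written, the SAP ignores a stated design feature, and for markers related to age or sex its patient-control p-values are conservative. Over the assumed correlations of 0 to 0.3, the unpaired interval ranges from about 2% narrower to 17% wider than the paired one, and the type I error from about 5.0% down to 2.1%. Under frequency matching, the precision forgone is about 2% to 16% for an explained variance of 5% to 30%. These figures rest on equal SDs, complete data, a two-sided 5% level and correlations that are assumed, not documented.

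With positive correlation the error is towards missing a difference, not towards a false one. The comparison supports the two numbered objectives without being either of them. This is a cheap improvement, not a flaw that threatens the trial's main conclusions.

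**What to change.** In the SAP, state whether controls are matched by pair or by frequency, and name the visit at which patients are compared with them. Replace the unadjusted patient-control test with a linear regression of each marker on group, age and sex, on the log scale if the marker is skewed. If matching is one to one, record the pair number and use a paired t-test instead, or the Wilcoxon signed-rank test.

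The cost is a few lines of SAP text and, for pairs, one data column; age and sex are already needed for the matching. The statistical price is fewer degrees of freedom: two for the regression (58 to 56), and 29 for the paired test, whose interval is about 2% wider if the correlation is zero. A paired test also drops a pair when either member's value is missing.

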(1) Do different lipid-lowering drugs (simvastatin monotherapy and ezetimibe/simvastatin combination therapy) have a different impact on the lipid profile, oxidative stress indices, Tryptophan degradation?

(2) Does statin monotherapy or co-administration of ezetimibe ameliorate the renal dysfunction in CKD patients?

(3) How do lipid-lowering therapy effect on lipidemia disorders in patients with CKD by mechanism involved in oxidative stress and tryptophan?

(4) Are the unexpected effects on muscle problem and hepatic enzyme profile of long-term statin monotherapy and statin/ezetimibe combination therapy a big concern?

II. REVIEW OF RESEARCH LITERATURE

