2.14. New York Heart Association class III (McMurray et al., 2012)

Classification of heart failure symptoms

Class I	People whose physical activity is not limited. Ordinary physical activity does not cause undue fatigue, heart palpitations, trouble breathing, or chest pain.
Class II	People who have some limitation on physical activity. They are comfortable at rest, but ordinary physical activity causes fatigue, heart palpitations, trouble breathing, or chest pain.
Class III	People who have a marked limitation on physical activity. They are comfortable at rest, but less-than-ordinary physical activity causes fatigue, heart palpitations, trouble breathing, or chest pain.
Class IV	People who are unable to carry on any physical activity without discomfort. Symptoms may be present even at rest. If any physical activity is done, discomfort increases.

2.15. 2017 Taiwan lipid guidelines for high-risk patients

LDL-C increased CV risk in patients with CKD. In adults with glomerular filtration rate (GFR) < 60 mL/min/1.73m² without chronic dialysis (CKD stage 3-5), statin therapy should be initiated if LDL-C ≥ 100 mg/dL. Ezetimibe can be added to a statin to consolidate the CV protection in CKD patients (Li et al., 2017)

3. Objective of the research

The target of this study is to focus on mechanisms underlying dyslipidemia in CKD and clinical trial evidence for lipid lowering therapy in patients with CKD via parameters of lipid, oxidative stress, tryptophan degradation as well as renal function, in comparison to statin/ezetimibe therapies in CKD patients with dyslipidemia.

- 1) To verify the effect of lipid lowering therapies on lipid profile and inflammatory status in Vietnamese CKD population. [Time Frame: at the baseline and at 4th month, and one-year following].
- 2) To compare the effect of lipid-lowering regimes (simvastatin mono-therapy and EZE/simvastatin 10/20, EZE /simvastatin 10/40 combination therapy) on lipid profile, oxidative stress indices, Tryptophan degradation, renal parameter, and side effect in Vietnamese CKD patient. [Time Frame: after the 4th month, 8th month and one-year following].

We hope with scientific evidence, doctors will well understand the mechanism, effect, and safety of potential and existing therapies. Therefore, the prescription rate of lipid-lowering drugs and control rate of hyperlipidemia could be increased in CKD

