4.6. Procedure

- Potentially eligible patients attended a screening visit in an internal examination room or internal department of Hue University Hospital for medical history and other eligibility criteria checked.

- Fasting blood samples will be taken for local laboratory assays lipid profile, proteinuria, urea and creatinine, creatine kinase, SGOT, SGPT, total blood count, total haemostasis test

- If the patient satisfies the including criteria, written informed consent obtained 30 enrolled patients will be randomized into 3 groups and will receive one of 3 lipid-lowering therapies at the baseline and continue for 12 months

Group 1: (10 participants) receive 40 mg/day simvastatin (patient No 1, 4, 7...)

Group 2: (10 participants) receive ezetimibe/simvastatin 10/20 mg/day: (patient No 2, 5, 8...)

Group 3: (10 participants) receive ezetimibe/simvastatin 10/40 mg/day: 10/40: (patient No 3, 6, 9...)

- Patients will follow the treatment for 12 months and will be seen in the study clinics for routine follow-up checks and blood test at 4, 8, and 12 months.

- At each follow-up time, study treatment will be continued, unexplained muscle pain and non-study treatment recorded.

Patients are asked for an unscheduled visit if they want to have any additional review.

- If patients are unable or unwilling to attend the follow-up checks, ask them if they have any serious adverse events.

- The blood samples will be sent to Biochemical Department of Sassari University for oxidative stress indices and Tryptophan degradation indices every 4 months.

5. Biochemical analysis

- Serum Creatinine, GFR, urine protein, lipid profile, SGOT, SGPT, CK (Total Cholesterol, LDL-C, HDL-C, TG): Will be done in Hue University hospital/Hue Central Hospital.

+ Total Cholesterol, LDL-C, HDL-C, and TG were measured by enzymatic methods using commercial kits (Boehringer-Mannheim, Mannheim, Germany): Patients must fast for at least 12 hours before the test

+ Serum CK levels were measured by using a fully automated biochemical analyzer (Abbot).

+ Proteinuria

+ Serum urea, creatinine

+ Total cells blood count

+ Total hemostasis test

[Time Frame: at baseline and 4, 8, 12 months of treatment]

- Serum concentrations of Oxidative stress indices (MDA, All/UA, Taurine), Trp degradation indices (Kyn, Trp, Kyn/Trp ratio): Will be done in Sassari University hospital.

MDA, All/UA ratio, taurine, Kyn, Trp were determined by capillary electrophoresis UV detection.

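### The SAP's test for differences in the effect of each therapy looks only within one arm, and no planned analysis compares change from baseline between the three regimens

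*SAP*

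**What the plan says.** The protocol asks a comparative question. Research question 1 (section I) is whether the drugs "have a different impact on the lipid profile, oxidative stress indices, Tryptophan degradation". Objective 2 (section 3) is "To compare the effect of lipid-lowering regimes (simvastatin mono-therapy and EZE/simvastatin 10/20, EZE /simvastatin 10/40 combination therapy) on lipid profile" and further markers. Objective 1 concerns change under treatment: "To verify the effect of lipid lowering therapies on lipid profile and inflammatory status in Vietnamese CKD population".

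The SAP has two paragraphs on the treated patients:

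- Third paragraph: "The statistical differences in the effect of each therapy on laboratory mean values will be evaluated by one way repeated measure ANOVA with Bonferroni correction", with Dunnett T3 offered as an alternative correction.
- Fourth paragraph: "To compare the differences in the median values of laboratory tests between 3 groups, ANOVA one-way will be applied". Pairwise testing then follows: "If there are statistical differences between 3 groups, we will use deeply ANOVA one-way test to analyze which group is different from another group", using Bonferroni or Dunnett T3 according to the Levene test.

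The fourth paragraph names no visit and does not mention baseline. No arm-by-visit term appears in the SAP. Protocol section 4.6 gives 10 patients per arm, and section 5 gives measurements at baseline and months 4, 8 and 12.

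**The concern.** The only SAP sentence about differences in effect names a test with no arm factor. Its null hypothesis is that the visit means within one arm are equal. It rejects because a regimen changes a marker, whatever the other regimens do.

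The wording does not settle which comparison is meant. Dunnett T3 is a procedure for independent groups with unequal variances. Its presence in a repeated-measures sentence suggests that within-arm and between-arm comparison have been mixed.

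What is at stake is the comparative conclusion. With 10 patients per arm, a marker could reach significance in one arm and miss it in another although the regimens act alike. A report could then say that one regimen improves oxidative stress or tryptophan degradation and another does not. The SAP has no rule on which result may support such a statement.

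**Working it through.** The documents give no alpha for treatment tests, effect size, SD, visit correlation or sample-size calculation, so there is no planned figure to reproduce.

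**Inputs from the documents.** Three arms of n = 10 (Protocol 4.6); k = 4 visits (Protocol 5).

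**Assumptions.** Alpha 5% per test; normal data; the same shift d at months 4, 8 and 12 in every arm, in SDs of a single-visit value; equal correlation ρ of 0.5 or 0.7 between visits; no dropout.

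**Step 1: what each test can detect.**

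| SAP paragraph | Factor | Null hypothesis | Shows that regimens differ in effect? |
|---|---|---|---|
| Third | Visit, within one arm | No change over time in this arm | No |
| Fourth | Arm | Equal mean laboratory value in the 3 arms | Only indirectly: no visit named, baseline unused |

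**Step 2: power of the within-arm test.** It uses F with k − 1 = 3 and (k − 1)(n − 1) = 27 degrees of freedom. The visit means are 0, −d, −d, −d. Their squared deviations sum to (0.75d)² + 3(0.25d)² = 0.75d². The residual variance is 1 − ρ, so the noncentrality is 10 × 0.75d² / (1 − ρ). At ρ = 0.5 this is 15d².

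**Step 3: chance of mixed verdicts.** If each of three independent, identical arms is significant with probability p, the chance that one or two are significant is 1 − p³ − (1 − p)³ = 3p(1 − p). The maximum is 75%, at p = 50%. At ρ = 0.5 and d = 0.5, p = 0.296 and the chance is 3 × 0.296 × 0.704 = 62%.

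**Step 4: simulation with the Greenhouse-Geisser correction.**

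| Common shift d | Per-arm p, ρ = 0.5 | Mixed verdicts, ρ = 0.5 | Mixed verdicts, ρ = 0.7 |
|---|---|---|---|
| 0 | 3% | 10% | about 10% |
| 0.4 SD | 15% | 39% | 56% |
| 0.6 SD | 35% | 68-69% | 73-74% |
| 0.8 SD | 59% | 72% | 38-39% |
| 1.0 SD | 82% | 44% | 8% |
| 1.5 SD | 99.6% | 1% | below 1% |

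Ranges are repeat runs. The formula agrees: at p = 0.59, 3 × 0.59 × 0.41 = 73%.

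**Step 5: between-arm tests with equal regimens.** In a companion simulation without the Greenhouse-Geisser correction, the SAP's 3-group ANOVA read at month 12 rejects 4.7-5.1% of the time. ANOVA on change from baseline rejects 4.8-5.2%, and the arm-by-visit interaction 4.7-5.3%.

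**Step 6: would the between-arm test stop a false claim?** At 0.6-0.8 SD and ρ = 0.5, 64-69% of simulated trials had mixed within-arm verdicts together with a non-significant between-arm test on month-12 change. Only a rule on which result counts prevents a claim in those trials.

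**Step 7: how to use baseline.** Relative to a visit variance of 1, the variance that drives the month-12 comparison is:

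| Analysis | Formula | ρ = 0.5 | ρ = 0.7 |
|---|---|---|---|
| Month-12 value | 1 | 1 | 1 |
| Change from baseline | 2(1 − ρ) | 1 | 0.60 |
| ANCOVA on baseline | 1 − ρ² | 0.75 | 0.51 |

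Raw change gains nothing at ρ = 0.5 and loses below it. ANCOVA has the smallest variance at both correlations (ignoring the one degree of freedom spent on the slope).

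**The case against.** The two SAP paragraphs can be matched to the two objectives: the repeated-measures ANOVA to change under therapy (objective 1), the 3-group ANOVA to the comparison of regimens (objective 2). On that reading nothing is misassigned. The protocol also says "30 enrolled patients will be randomized into 3 groups and will receive one of 3 lipid-lowering therapies", and comparing follow-up values between randomized arms is a valid test of unequal effects, with about 5% error at month 12.

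Much of this stands. A reader might infer that the SAP will call regimens different because one arm is significant and another is not, and that equal regimens would therefore often look different. The documents do not support that: the SAP states no such decision rule, and it has a separate between-arm test. Nor do they support the inference that a real LDL-C difference would go unseen, since the 3-group ANOVA exists to look for one. The mixed-verdict rates describe a misuse that the SAP leaves open, not its planned comparison.

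Two things remain. The third paragraph speaks of differences in effect while naming a test that cannot show differences between regimens. The fourth paragraph leaves visit and baseline handling open, so the comparison of change asked for in objective 2 is not specified.

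**Conclusion.** The point holds as a gap in specification. The repeated-measures ANOVA cannot show that regimens differ, and the one between-arm test is on laboratory values at an unnamed visit without baseline. It is not a finding that the planned between-arm test has inflated error; read at month 12, it does not.

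The size is conditional. If within-arm p-values were compared, mixed verdicts would arise in about 40-75% of trials with equal regimens at common shifts of 0.4-0.8 SD, and in about 1% or fewer at 1.5 SD. These figures rest on the assumed alpha, correlations, shape of effect and absence of dropout. The documents do not say which markers would show moderate effects. The change is worth making because it protects the trial's comparative question at almost no cost.

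**What to change.** Reword the third SAP paragraph along these lines: *Change over visits within each therapy will be described by repeated-measures ANOVA. These within-therapy results will not be used to state that regimens differ.*

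Add to the fourth paragraph: *Any statement that regimens differ in effect will rest on a between-arm comparison that accounts for baseline: ANCOVA of the month-12 value on arm and baseline value (or the arm-by-visit term of a repeated-measures model). It will be reported as the difference between regimens with its 95% confidence interval.*

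The pairwise step can keep Bonferroni. Dunnett T3 works on unadjusted group means, so it should be dropped from the repeated-measures sentence and would not carry over to the adjusted means.

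No new patients, visits or assays are needed. The cost is a little more analysis work, and fewer statements that only one regimen improved a given marker.

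### The within-therapy repeated-measures ANOVA has no missing-data rule or sphericity correction and allows Dunnett T3, which is for independent groups: precision falls once visits are missed, an uncorrected omnibus F can exceed 5%, and T3 loses power

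*SAP*

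**What the plan says.** The SAP evaluates the effect of each therapy on laboratory means by "one way repeated measure ANOVA with Bonferroni correction or Dunnet T3 correction, if appropriate". It gives no analysis set, no rule for missed visits, no sphericity test and no epsilon correction.

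A rule for choosing Dunnett T3 appears only in the next SAP paragraph, on the comparison of the three treatment groups: "with Bonferroni if Levene test ≥ 0.05 or Dunnet T3 if Levene test < 0.05". That comparison is between independent groups.

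Protocol section 4.6 says that "30 enrolled patients will be randomized into 3 groups" of 10 each. Section 5 sets the blood and urine measurements "at baseline and 4, 8, 12 months of treatment", so each patient has four measurements, three of them after baseline. On non-attendance, section 4.6 says: "If patients are unable or unwilling to attend the follow-up checks, ask them if they have any serious adverse events". Neither document states an attendance rate, significance level, effect size, standard deviation or within-patient correlation.

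**The concern.** Three things look wrong in one sentence of the SAP.

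- **Missed visits.** Classical repeated-measures ANOVA needs a complete row per patient, so one missed visit removes that patient's other visits too. With 10 per arm, each such loss matters. If attendance is related to response or tolerance, the remaining patients may also be a selected group.
- **Sphericity.** The univariate F test assumes that differences between all pairs of visits have equal variance. One untreated baseline followed by three on-treatment visits is a setting where this can easily fail.
- **Dunnett T3.** It compares independent groups with unequal variances. Visits in the same patients are correlated, and T3 ignores the correlation.

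At stake are the precision and the error rates of the within-therapy results.

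**Working it through.** The documents contain no power or precision calculation to reproduce, so the check uses their design figures and stated assumptions.

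**Inputs from the documents:** 10 patients per arm, four visits (Protocol sections 4.6 and 5).
**Assumed:** two-sided 5% level; SD = 1; a fraction q missing each follow-up visit independently; a range of correlation structures.

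**1. Patients left.** Complete rows per arm = 10 × (1 − q)³:
- q = 5%: 10 × 0.95³ = 8.57
- q = 10%: 10 × 0.90³ = 7.29
- q = 15%: 10 × 0.85³ = 6.14

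The chance that an arm loses at least one patient is 1 − [(1 − q)³]¹⁰, which is 79% at q = 5% and 96% at q = 10%.

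**2. Standard error of the baseline-to-month-12 change.** With equal correlation r between visits, the complete-case SE is √[2(1 − r)/n], where n is the number of complete rows. At r = 0.5 this is √(1/n). The available-data SE comes from the expected information summed over all missing-visit patterns, with the covariance treated as known.

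| q | complete-case SE | available-data SE | ratio |
|---|---|---|---|
| 0% | 0.316 | 0.316 | 1.00 |
| 5% | √(1/8.57) = 0.342 | 0.321 | 1.06 |
| 10% | √(1/7.29) = 0.370 | 0.327 | 1.13 |
| 15% | √(1/6.14) = 0.404 | 0.334 | 1.21 |

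The ratios are practically the same at r = 0.7. Averaging over the random number of completers and over other correlation structures gives larger excesses: 7-8%, 15-19% and 25-30%. The table is the cautious version.

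**3. Omnibus F without correction.** Simulated type I error, n = 10, nominal 5%:
- compound symmetry: 5.0%
- AR(1), 0.5: 5.8%; 0.7: 6.4%; 0.9: 7.2%
- on-treatment visits correlated 0.8 with each other and 0.4 with baseline: about 7%
- the same with 0.3 to baseline: 7.7%; with a baseline SD of 1.5 as well (epsilon 0.50): 8.9%, or 9.3% at n = 7

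Greenhouse-Geisser gives 2.8-5.1% over the structures simulated at n = 10 and n = 7. Paired t tests with Bonferroni over the six pairs of visits give a familywise error of 3.9-4.5%, including under strong non-sphericity.

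**4. Dunnett T3 applied to visits.** n = 10, equal correlation r, six pairs of visits; power is for a 1 SD change from baseline to month 12.

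| r | T3 familywise error | T3 power | paired Bonferroni power |
|---|---|---|---|
| 0 | 4.3% | 27% | 21% |
| 0.3 | 1.4% | 24% | 32% |
| 0.5 | 0.5% | 23% | 47% |
| 0.7 | 0.07% | 21% | 74% |

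T3 does better only when a patient's visits are uncorrelated, which is not to be expected of repeated laboratory values.

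**The case against.** The strongest reply is that these are omissions and not stated errors.

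- The SAP does not say that patients with a missed visit are dropped. That follows from the classical method.
- The SAP neither plans nor rules out an epsilon correction.
- The sentence in Protocol section 4.6 on non-attendance is an instruction for collecting adverse events, not a forecast. It shows that missed visits are foreseen, but gives no rate.
- Bonferroni is named in the same sentence, and T3 is conditional on being appropriate.

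All of this stands, and it limits the point. A reader might infer that the planned analysis inflates type I error in general. The documents do not support that: only an uncorrected omnibus F is affected, and only if sphericity fails. Bonferroni on paired differences is sound, and T3 errs in the opposite direction. A reader might also measure the harm by comparing full attendance with complete cases. That overstates it, because a mixed model loses data too: at 10% missed, its SE rises from 0.316 to 0.327.

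The gain from a mixed model is also measured against complete rows. A plain paired comparison of all patients with both baseline and month-12 values has an SE only 2-3% above the mixed model at 10-15% missed. A mixed model does not remove bias if data are missing not at random.

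What the reply does not answer is that T3 is named, with no rule in that sentence, for a comparison it does not fit, and that the SAP leaves both the handling of missed visits and the choice of F test to be settled after the data are seen.

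**Conclusion.** The point holds in a limited form, and the SAP should be changed.

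- **Precision:** the SE of the 12-month change is about 6%, 13% or 21% larger than with all available data at 5%, 10% or 15% missed per follow-up visit. The loss is nil with full attendance. The rates are assumptions, the covariance is treated as known and data are taken as missing at random, so the real gain from a mixed model would be somewhat smaller than under those conditions.
- **Omnibus F:** about 6-7% instead of 5% in the moderate structures and up to about 9% in the extreme ones, if no correction is applied. There is no inflation under compound symmetry.
- **Dunnett T3:** wrong for visits in the same patients. With positively correlated visits it is very conservative and can halve power or worse (23% against 47% at r = 0.5).

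Bias from selective attendance is possible, but the documents contain nothing that would show it or its size.

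**What to change.** Replace the sentence with one linear mixed model per marker, fitted to all arms and all available visits:

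- baseline as one of the outcome visits, and not also as a covariate;
- terms for visit, arm and arm-by-visit;
- unstructured covariance pooled across the three arms;
- a small-sample degrees-of-freedom method. If the software version named in the SAP does not offer one, use single-degree-of-freedom contrasts or other software;
- planned contrasts: Bonferroni-adjusted change from baseline within each arm, and arm differences in change at month 12.

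The pooling and the small-sample method matter. With complete data and 10 per arm, a Wald omnibus visit test within an arm rejects at 6.5% (F with 3 and 27 df) or 9.0% (chi-square) with pooled covariance, and at 10.4% or 19.9% with covariance estimated per arm. Without this care the replacement would bring back the error that an uncorrected F can have.

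Delete Dunnett T3 from the within-patient sentence. If repeated-measures ANOVA is kept as a check, report Greenhouse-Geisser p-values.

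The arm-by-visit term also serves the comparison of regimens in Protocol section 3, objective 2, which a within-arm ANOVA cannot do.

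Cost: SAP wording only, no new data. The model is slightly more complex and relies on data being missing at random, which the SAP should state.
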